#### 3.4 Inclusion criteria

Participants must fulfill all of the following criteria in order to be eligible for the study:

- 1. The participant or legal guardian is willing and able to understand, sign and date the Ethics committee approved study specific Informed Consent Form.
- 2. The participant is a male or female between the ages of 12 and 65 (inclusive).
- 3. The participant has a history of the following:
  - O No more than mild to moderate far-sightedness or near-sightedness (i.e. Spherical equivalent refraction (SER) between +10 to -15).
  - o an astigmatism of 2.5D or less.
  - o an anisometropia of 1.5D or less.
- 4. The participant is free of ocular and systemic abnormalities that might affect visual functions.

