# 7.3 Primary Effectiveness Endpoint

The primary effectiveness endpoint is to demonstrate that the LFR-260 is within 0.5D (+/-) in measuring sphere and cylinder results and within 10 degrees for axis results among subjects with low astigmatism and within 5 degrees among subjects with moderate to high astigmatism from the traditional phoropter in a very large proportion of subjects.

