# 7.7 Other Planned Analyses

#### 7.7.1 Bland-Altman Agreement Analysis

Supporting analyses will evaluate the distribution of paired differences between LFR-260 and reference for the three dimensions (sphere, cylinder, and axis) using Bland-Altman agreement analysis. This will include determination of the standard deviation of paired differences, the 95% limits of agreement, and an evaluation of systematic bias. The Bland-Altman plot of paired differences versus the mean of measurements will be provided. The relationship between bias and the mean of measurements will characterized. The same analysis will be applied to the vector difference between LFR-260 measurements and the gold standard in terms of sphere and cylinder measurements. The vector differences is square root of (X1-Y1) + (X2-Y2) where the X1 and X2 are measurements of sphere and cylinder using the investigational devices and Y1 and Y2 are the same measurements using the gold standard.

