# 7.7.2 Poolability and Homogeneity of Treatment Effects

Homogeneity of treatment effects across sites will be evaluated by comparing differences between the LFR-260 and the gold standard separately for sphere, cylinder, and axis and also for the vector analysis of sphere and cylinder.

Similarly, differences between measurements from the investigational device and the gold standard device will be summarized by gender, age category, race, and ethnicity to investigate consistency or heterogeneity of the treatment effect across those subgroups, separately for sphere, cylinder, and axis and also for the vector analysis of sphere and cylinder.

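### As written, the axis limits of agreement are not split by astigmatism, so they would describe neither tier of the primary endpoint and react weakly to error in moderate-to-high astigmatism

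*Combined protocol and SAP*

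**What the plan says.** Section 7.7.1 evaluates paired differences "for the three dimensions (sphere, cylinder, and axis) using Bland-Altman agreement analysis". The output is "determination of the standard deviation of paired differences, the 95% limits of agreement, and an evaluation of systematic bias". On plotting, the section states: "The Bland-Altman plot of paired differences versus the mean of measurements will be provided". It adds: "The relationship between bias and the mean of measurements will characterized". For axis that mean is an orientation in degrees. No astigmatism stratum is named, and cylinder power is not a plotting variable for axis. The vector analysis in the same section does not fill the gap, because it is built from two components only, "where the X1 and X2 are measurements of sphere and cylinder using the investigational devices".

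Section 7.7.2 compares axis differences across sites and says that differences "will be summarized by gender, age category, race, and ethnicity". Astigmatism level is not on that list.

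The primary endpoint in section 7.3 does distinguish: "within 10 degrees for axis results among subjects with low astigmatism and within 5 degrees among subjects with moderate to high astigmatism". Sections 2.5.1 and 7.4 say the same. Section 3.4 admits "an astigmatism of 2.5D or less" with no lower bound, so eyes with little or no cylinder enter the axis analysis. No section gives the dioptre value that separates the tiers, and the Statistical Considerations in the synopsis print low astigmatism against both tolerances.

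**The concern.** By setting two axis tolerances, the plan accepts that a given number of degrees means different things at different cylinder powers. The agreement analysis then drops that distinction. When groups with unequal scatter are pooled, the one with the larger scatter dominates the SD, so low-astigmatism eyes would largely set the limits. A reader of the axis limits could not tell how the device performs in moderate-to-high astigmatism, where the plan's own tolerance is tightest. The planned relation of bias to the mean cannot reveal this, because mean axis carries no information about cylinder power.

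**Working it through.** **1. The plan's own figure.** The only design figure is the power in section 7.5 (216 eyes, true proportion 0.90, goal 0.80, one-sided exact alpha 0.05). The smallest passing count is 183 of 216 (84.7%), with attained alpha 0.0461 and power 0.9946. The stated 99% reproduces. No figure is given for the Bland-Altman analysis, so the inputs below are assumptions.

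**2. Pooled limits using the plan's 10:5 ratio.** Assume no bias, and let each tier's 95% limits just meet its own tolerance: SD low = 10/1.96 = 5.1, SD higher = 5/1.96 = 2.55 degrees. With p the share of low eyes,

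pooled limits = ±1.96 × √(p × SD_low² + (1 − p) × SD_high²).

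- At p = 0.70: 0.7 × 26.01 + 0.3 × 6.50 = 18.21 + 1.95 = 20.16; √20.16 = 4.49; limits ±8.8. Low eyes supply 18.21/20.16 = 90% of the variance.
- Double the higher-tier SD to 5.1: 18.21 + 0.3 × 26.01 = 26.01; √26.01 = 5.1; limits ±10.0.
- Higher-tier eyes beyond 5 degrees: 2 × (1 − Φ(5/2.55)) = 5% before, and 2 × (1 − Φ(5/5.1)) = 33% after.

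Range over the assumptions, before and after that doubling:

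| SD low | 50% low eyes | 70% low eyes | 85% low eyes |
|---|---|---|---|
| 5.1 | ±7.9 to ±10.0 | ±8.8 to ±10.0 | ±9.4 to ±10.0 |
| 10 | ±14.3 to ±15.6 | ±16.6 to ±17.3 | ±18.2 to ±18.5 |
| 15 | ±21.1 to ±22.0 | ±24.7 to ±25.2 | ±27.2 to ±27.4 |

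The shift is about 0.2 to 2.1 degrees throughout. Pooling also dilutes a systematic error: at 70% low eyes, a 5 degree shift confined to the higher tier appears as a pooled bias of 0.3 × 5 = 1.5 degrees.

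**3. Why scatter should differ.** An axis difference θ at cylinder C leaves a residual cylinder of 2C sin θ. A residual of 0.25 D corresponds to 30 degrees at C = 0.25 D, 7.2 degrees at 1 D and 2.9 degrees at 2.5 D.

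**4. Equal dioptric noise at a level that fits section 7.5.** A true joint agreement of 0.90 needs axis-only agreement of at least 0.90. Simulation assumptions: noise SD 0.025 D per cross-cylinder component per reading, low tier 0.25 to 0.75 D, higher tier 1 to 2.5 D, 70% low eyes, differences taken the short way round 180 degrees. Axis-only agreement is about 94%. The limits are about ±10.9 low and ±2.6 higher. Pooled: √(0.7 × 10.9² + 0.3 × 2.6²) = √(83.2 + 2.0) = ±9.2. Doubling the higher-tier error takes its own limits to ±5.2, past its tolerance; the pooled limits become √(83.2 + 0.3 × 5.2²) = √91.3, about ±9.6.

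**5. What the primary proportion would show.** In step 2 after doubling, axis-only agreement is 0.7 × 0.950 + 0.3 × 0.673 = 0.867, down from 0.950. If every eye also meets sphere and cylinder and eyes are independent, the primary test still passes about 83% of the time.

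**The case against.** **Nothing is decided on this analysis.** Section 7.7.1 calls it supporting and sets no acceptance limit. The decision rule in section 7.6 applies to an endpoint that already scores axis by tier, so a higher-tier error beyond 5 degrees counts as a failure there. This stands, and it limits the weight of the point. It does not remove it: no tier-specific proportion is planned, and step 5 shows that a fault affecting a third of higher-tier eyes could still pass. The supporting limits would then be the natural place to see it.

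**Pooling is inferred from silence.** The text neither says that all eyes are combined nor rules out stratified output. This stands, so the point is conditional on the plain reading.

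**The planned plot is the standard form.** Mean axis can show a bias that depends on orientation, so the plot should be kept. What is missing is a second plot.

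Two stronger readings are tempting, but the documents do not support them:

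- A reader might infer that pooled limits would be far wider than both tolerances. That depends on the noise assumed. At 0.05 D per component the pooled limits are about ±20 degrees, but axis-only agreement is then about 78%, below the 0.80 goal and at odds with the 0.90 in section 7.5. At 0.025 to 0.03 D (agreement about 94% to 91%) they are about ±9.2 to ±11.2.
- A reader might infer that site and subgroup axis differences would mainly reflect who has little astigmatism. Symmetric scatter widens the spread and lowers precision, but it does not shift a mean signed difference.

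**Conclusion.** The point holds as a modest improvement to a supporting analysis. Read plainly, sections 7.7.1 and 7.7.2 summarise axis across eyes whose precision the primary endpoint treats as different. The resulting limits fit neither tier: ±8.8 degrees against ±10.0 and ±5.0 in step 2, and ±9.2 against ±10.9 and ±2.6 in step 4. Doubling the higher-tier error moves them by only 1.2 and about 0.4 degrees respectively. The direction needs only that axis scatter is larger at low cylinder, as the two tolerances imply. The size rests on assumed SDs, tier boundaries and case mix, none of which the documents give. It would be wrong to infer that the primary conclusion is at risk from this: the pass rule, its alpha and its 99% power do not depend on the Bland-Altman analysis.

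**What to change.** - **Section 7.7.1, by tier.** Report axis bias, SD and 95% limits separately for the two astigmatism tiers of the primary endpoint. Assign each eye by its phoropter cylinder, using the same dioptre cut-off that scores the primary endpoint. State that cut-off, and reconcile the synopsis, where both tolerances are labelled low astigmatism.
- **Zero cylinder.** Exclude from the axis summary, and count, eyes with zero cylinder, whose axis is undefined.
- **Plot.** Keep the plot against mean axis. Add one of axis difference against phoropter cylinder, with the 10 and 5 degree lines drawn.
- **Section 7.7.2.** Give axis summaries within tier where numbers allow.

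No new data are needed, and the cut-off is required for the primary endpoint anyway. The cost is one more table and plot, and less precise limits per tier. For example, 30% of 216 is about 65 eyes. With SD 2.55, the standard error of a limit is about 2.55 × √((1 + 1.96²/2)/65) = 0.54 degrees, so its 95% interval is about ±1.1 degrees if eyes are treated as independent.

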# 1.2 Device Name and Intended Use

The LFR-260 is intended to be used for distance vision testing in any environment, may it be in optometric clinics or in the field outside of the clinic, because of its compact form factor and portability.

The LFR-260 is an application-controlled instrument providing capabilities for distance vision testing including sphere, cylinder, and axis. The visual acuity and eye subjective manifest refraction determination will always be administered by an eye care professional (ECP) licensed and registered by the appropriated body in the region intended to be used. The instrument is designed in a way that it will only work with approved personnel and the use of secure credentials.

The device is intended to be used in patients aged from 12-65 years old with healthy visual systems and a refractive error no bigger than (+10 to -15D) and astigmatism no bigger than 2.5D (if any).

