# 2.5 Hypotheses

# 2.5.1 Primary Effectiveness Hypothesis

The primary hypothesis for this study is that the probability of simultaneously achieving good clinical agreement for sphere, cylinder, and axis exceeds a performance goal (PG) for measurements made by the LFR-260 compared to those obtained using traditional phoropter. The *a priori* PG is 0.80. Good clinical agreement is defined as a sphere and cylinder measurements that are within +/- 0.5 D and within 10 degrees for axis among subjects with low astigmatism and within 5 degrees among subjects with moderate to high astigmatism.

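### The Bland-Altman plan relates bias, but not scatter, to refractive power, so one pooled pair of limits for sphere over +10 to -15 D rests on an unchecked constant SD

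*Combined protocol and SAP*

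**What the plan says.** Section 7.7.1 lists the Bland-Altman outputs for sphere, cylinder and axis: "This will include determination of the standard deviation of paired differences, the 95% limits of agreement, and an evaluation of systematic bias". It adds a graph, "The Bland-Altman plot of paired differences versus the mean of measurements will be provided", and one statement about magnitude, "The relationship between bias and the mean of measurements will characterized". The same analysis is to be applied to a sphere-cylinder vector difference.

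The plan does not itself call the limits single or constant. That follows from its naming one SD and one set of limits per dimension, with no model for spread, no transformation and no limits by power band. Section 7.7.2 examines differences by site, gender, age category, race and ethnicity, but not by refractive power.

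The range is wide. Section 3.4 admits "Spherical equivalent refraction (SER) between +10 to -15", and section 1.2 gives the intended use as "a refractive error no bigger than (+10 to -15D) and astigmatism no bigger than 2.5D (if any". The agreement tolerance in section 2.5.1 is the same at every power: "Good clinical agreement is defined as a sphere and cylinder measurements that are within +/- 0.5 D".

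**The concern.** Limits computed as mean difference ± 1.96 SD hold about 95% of differences at every power only if the SD is the same at every power. Over a 25 D span that should be checked rather than presumed. The range crosses zero, so scatter that grows with absolute power would appear as a V (a bow-tie of points) around zero on the planned plot. Relating bias to the signed mean does not measure that pattern.

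At stake is how the supporting agreement figure reads. Pooled limits could lie inside 0.5 D because most enrolled eyes have low power, while a material share of high-power eyes within the intended use falls outside 0.5 D. The point is mainly about sphere, since cylinder is capped at 2.5 D and axis is an angle.

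**Working it through.** **The plan's own figure.** Section 7.5 states 99% power for 216 eyes, performance goal 0.80, true proportion 0.90 and one-sided alpha 0.05. With eyes taken as independent, as the plan does, the exact test rejects at 183 or more successes (exact alpha 0.0461, power 0.9946). The figure reproduces. It does not depend on the limits of agreement, for which the plan states no number.

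**Inputs.** From the documents: the range +10 to -15 D and the 0.5 D tolerance. Assumed, because the documents give neither: no bias; normal differences with SD(p) = s0 + k|p|, s0 = 0.20 D and k = 0 to 0.04; and two power mixes, uniform from -15 to +10 D, and normal with mean -1.5 D and SD 3 D.

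**Formulas.** Pooled half-width L = 1.96 × sqrt(E[SD(p)²]). Coverage at power p = 2Φ(L/SD(p)) − 1. Correct half-width at p = 1.96 × SD(p).

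**One case by hand** (uniform mix, k = 0.02).
- E|p| = (15²/2 + 10²/2)/25 = 6.5 and E[p²] = (15³ + 10³)/75 = 58.33.
- Pooled variance = 0.04 + 2 × 0.20 × 0.02 × 6.5 + 0.0004 × 58.33 = 0.1153, so SD = 0.340 and L = 0.67 D.
- At 1 D: SD 0.22, correct limits ±0.43 D, coverage 2Φ(3.03) − 1 = 99.8%.
- At 12.5 D: SD 0.45, correct limits ±0.88 D, coverage 2Φ(1.48) − 1 = 86%.

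**Range over assumptions** (coverage averaged over the eyes in each band):

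| Power mix | k | Pooled limits | Coverage below 2 D | Coverage at 10-15 D |
|---|---|---|---|---|
| either | 0 | ±0.39 D | 95% | 95% |
| uniform | 0.01 | ±0.53 D | 99% | 89% |
| uniform | 0.02 | ±0.67 D | 99.7% | 86% |
| uniform | 0.04 | ±0.96 D | 99.98% | 83% |
| normal | 0.01 | ±0.45 D | 97% | 85% |
| normal | 0.02 | ±0.50 D | 98% | 77% |
| normal | 0.04 | ±0.62 D | 99% | 67% |

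Point check on the 77%: at 11 D the SD is 0.20 + 0.02 × 11 = 0.42, 0.503/0.42 = 1.20, and 2Φ(1.20) − 1 = 77%. Coverage over all eyes stays at 94-95% in every row, so the pooled figure gives no warning.

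**Can pooled limits look acceptable while high-power eyes do not?** Assume SD = 0.15 + 0.02|p|, with 85% of eyes uniform on 0-4 D and 15% uniform on 4-15 D of absolute power.
- E|p| = 0.85 × 2 + 0.15 × 9.5 = 3.125.
- E[p²] = 0.85 × 16/3 + 0.15 × (3375 − 64)/33 = 19.58.
- Variance = 0.0225 + 0.006 × 3.125 + 0.0004 × 19.58 = 0.0491, so L = 0.43 D, inside 0.5 D.
- Correct limits at 1, 10 and 15 D: ±0.33, ±0.69 and ±0.88 D.
- Coverage of the pooled limits: 99%, 79% and 67%.
- Share of eyes more than 0.5 D off, 2(1 − Φ(0.5/SD)): 0.3%, 15% and 27%.

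**Would 216 eyes reveal it?** The check is a regression of absolute residuals on absolute mean power, in simulation with robust standard errors and independent eyes. At slope 0.02 it detects the pattern in about 96% of trials under the 85/15 mix, 74% under the normal mix with SD 3 D, and 52% with SD 2 D. In the last case about 3 eyes lie beyond 6 D. The fitted limits at 10 D then ran from 0.51 to 1.10 D in 95% of trials, against a correct 1.96 × 0.40 = 0.78 D.

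**The case against.** The strongest objection is that nothing in the documents shows scatter growing with power. They mention a tunable lens (section 4.2) but give no error model, no SD and no distribution of power. Every harmful figure above comes from an assumed slope, and at slope 0 the plan is right. This stands, and it makes the point conditional.

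A reader might infer that the primary conclusion or its 99% power is in doubt. The documents do not support that. Section 7.7.1 is labelled supporting, and the decision in section 7.6 rests on an exact binomial bound that assumes nothing about constant SD. An eye more than 0.5 D off on sphere is a failure at any power.

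A reader might also infer that the limits are the only measure of error in dioptres. They are not: the plan also has the SD, the bias, the vector difference and the differences by site and subgroup. None of these is examined by power.

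Nor is the plan blind to fanning, because the difference-versus-mean plot is where one would look for it. What is missing is an analysis that follows from the plot, so any choice of alternative limits would be made after seeing the data.

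Finally, a test of spread may miss the pattern when few high-power eyes are enrolled, as the 52% shows. That is a reason to report power-dependent limits with their uncertainty in every case, rather than only after a significant test.

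**Conclusion.** The point holds in a conditional and limited form. The plan relates bias but not scatter to power, and has no set analysis if scatter varies. For sphere, if the SD rises by 0.01 to 0.04 D per dioptre of absolute power from a base of 0.20 D, pooled 95% limits cover about 97-100% of eyes below 2 D and about 67-89% at 10-15 D, under the two power mixes assumed. If the SD is constant, the planned limits are correct. The sizes are illustrative. The documents do not establish that this device's error depends on power, and the primary test is untouched. This is a worthwhile, cheap improvement to a supporting analysis.

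**What to change.** In section 7.7.1, add that after any bias trend is removed, absolute residuals will be regressed on absolute mean sphere power and, secondarily, on mean cylinder power for cylinder, with standard errors clustered by subject because both eyes contribute. Power-dependent limits are then fitted mean ± 1.96 × sqrt(π/2) × fitted absolute residual, that is ± 2.46 × fitted absolute residual.

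Report these limits with confidence intervals in every case, next to the pooled limits, so that no threshold for a meaningful slope has to be chosen. Tabulate them only at powers within the enrolled range, and label the pooled limits as an average over the enrolled powers.

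The cost is a few lines of text and one extra regression each for sphere and cylinder, on data already collected. The downside is that limits at high power will be imprecise if few such eyes are enrolled, and may look less favourable than the pooled figure.

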# 7.7.4 Reliability and Repeatability Analysis

Reliability of LFR-260 will be conducted in a subset of subjects for which measurements will be obtained twice in an office context. This analysis will be repeated in a remote context. Reliability will be evaluated using intraclass correlations for each of the continuous measurements, sphere, cylinder, and axis and for the vector measurement of sphere and cylinder.

For a subset of 33 subjects (66 eyes), the LFR-260 device will be measured again approximately 60 minutes after the initial assessment in order to measure the repeatability/accuracy of the device.

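### The sphere-cylinder vector difference is printed without squares, Bland-Altman does not suit it even with them, and the vector value for the ICC is not defined

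*Combined protocol and SAP*

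**What the plan says.** Section 7.7.1 defines the quantity in words: "The vector differences is square root of (X1-Y1) + (X2-Y2"), where "X1 and X2 are measurements of sphere and cylinder using the investigational devices" and Y1 and Y2 are the same readings on the phoropter. The Statistical Considerations part of the synopsis gives the same definition. Axis does not enter it.

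Three sets of analyses use the vector:

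- **Bland-Altman (7.7.1).** "The same analysis will be applied to the vector difference between LFR-260 measurements and the gold standard in terms of sphere and cylinder measurements". That analysis consists of "the standard deviation of paired differences, the 95% limits of agreement, and an evaluation of systematic bias", and "The Bland-Altman plot of paired differences versus the mean of measurements will be provided".
- **Site and subgroup comparisons (7.7.2 and synopsis).** These are to be done "separately for sphere, cylinder, and axis and also for the vector analysis of sphere and cylinder".
- **Reliability (7.7.4).** Intraclass correlations are planned for sphere, cylinder and axis, "and for the vector measurement of sphere and cylinder". The synopsis lists ICCs for the three separate components only.

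No section says how a vector value is formed from one reading on one device.

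**The concern.** Taken literally, the formula is the square root of a signed sum. It has no value when the sum is negative, it lets opposite errors cancel, and its unit is the square root of a dioptre. The plan has no rule for an eye with a negative sum.

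The likely intention is the Euclidean distance, but restoring the squares does not make the planned analyses fit. Bland-Altman needs a signed difference that centres on zero when there is no bias, and one value per device to average for the horizontal axis of the plot. A distance offers neither. An ICC needs one value per reading, whereas the formula gives one value per device-reference pair.

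The vector is one of four quantities (with sphere, cylinder and axis) carried through the supporting analyses. As the text stands, the analyst would have to choose a formula, a rule for negative sums and a per-reading value, possibly after seeing the data.

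**Working it through.** **Inputs.** The formula and its uses come from the synopsis and sections 7.7.1, 7.7.2 and 7.7.4. The plan gives no figure for the vector to reproduce. Its one computed figure, 99% power in section 7.5, does reproduce: with 216 eyes treated as independent, success needs at least 183, with exact alpha 0.046 and power 0.995. It does not involve the vector.

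Write dS = X1 - Y1 and dC = X2 - Y2.

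**Step 1: single eyes.**

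| dS, dC (D) | Printed: sqrt(dS + dC) | With squares: sqrt(dS^2 + dC^2) |
|---|---|---|
| -0.25, -0.25 | sqrt(-0.50), undefined | 0.35 D |
| -0.50, +0.25 | sqrt(-0.25), undefined | 0.56 D |
| +0.50, -0.50 | 0 | 0.71 D |
| +0.25, 0 | 0.50 | 0.25 D |

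**Step 2: how often the printed form fails.** The documents give no SD of differences, so the following is assumed: dS and dC normal and independent with equal SD, rounded to 0.25 D steps.

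| SD (D) | Undefined, no bias | Undefined, sphere bias +0.25 D | Undefined, sphere bias -0.25 D |
|---|---|---|---|
| 0.15 | 28% | 5% | 72% |
| 0.3 | 39% | 19% | 61% |
| 0.5 | 43% | 30% | 57% |

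A further 8% to 12% of eyes score exactly zero although the readings differ; 87% to 100% of those are within 0.5 D on both components.

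The results move with the correlation between dS and dC. From -0.6 to +0.3, the zero share runs from about 4% to 22.5%. At -0.6, with the same biases, the undefined share runs from about 1% to 79%.

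**Step 3: Bland-Altman with squares restored.** The same assumptions apply, with no true bias; limits are mean ± 1.96 SD of the distance.

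| SD (D) | Mean distance | SD of distance | Limits (D) |
|---|---|---|---|
| 0.15 | 0.18 | 0.146 | -0.10 to 0.47 |
| 0.3 | 0.38 | 0.214 | -0.04 to 0.80 |
| 0.5 | 0.63 | 0.335 | -0.03 to 1.29 |

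The mean is well above zero with no bias, and each lower limit is a value that a distance cannot take. Direction is lost too: at SD 0.3 D, sphere biases of +0.25 D and -0.25 D both give a mean of 0.44 D.

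**Step 4: the plot and the ICC.** The plot needs a vector value for the LFR-260 and one for the phoropter, so that they can be averaged. The ICC needs a vector value for each LFR-260 reading. The only formula in the plan already combines two devices into one number, so neither input exists.

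**The case against.** The strongest reply is that the missing squares may not be in the source at all. The available text was converted from PDF, and the indices appear there as plain X1 and Y1, so an exponent could have been flattened. The identical wording in the synopsis proves little, because both passages went through the same conversion. A superscript does survive in the study flowchart, but that is not conclusive. If the source has the squares, every share in Step 2 falls away. If it does not, a programmer would meet the first negative sum and notice.

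The sizes also rest on assumed SDs, and the upper ones describe a poor device. At SD 0.4 and 0.5 D with no bias, only about 78% and 62% of eyes would be within 0.5 D on both sphere and cylinder before axis is considered. Both are below the 0.80 performance goal. At SDs of 0.15 to 0.3 D the undefined share is 28% to 39%.

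The scope is limited too. Signed Bland-Altman analyses and ICCs for sphere, cylinder and axis are planned separately, so bias and its direction are still assessed. Section 7.7.2 asks only that differences be compared and summarised by site and subgroup, which a distance with squares allows.

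All of this stands as a limit on the size and reach of the point. It does not answer the two defects that survive any typographical repair. The spherical equivalent recorded under section 4.3 is one value per reading, but the plan does not call it the vector.

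**Conclusion.** The concern holds, at the level of something that should be corrected. As printed, the formula cannot be computed for a substantial share of eyes: 28% to 43% under independent, unbiased differences with SDs of 0.15 to 0.5 D in 0.25 D steps, and 5% to 72% if a sphere bias of up to 0.25 D either way is allowed. Those shares depend on assumed SDs and apply only if the source file really lacks the squares; so does the problem with the site and subgroup summaries.

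Two findings need neither condition. Bland-Altman bias, limits and the difference-versus-mean plot do not suit a distance, and the vector ICC in section 7.7.4 has no defined input. The primary test against 0.80 (sections 7.4 to 7.6) and the separate sphere, cylinder and axis analyses are unaffected.

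**What to change.** 1. Check the source file for a lost exponent. If there is none, correct the synopsis and section 7.7.1 to sqrt((X1 - Y1)^2 + (X2 - Y2)^2).
2. In section 7.7.1, restrict bias, limits of agreement and Bland-Altman plots to signed components. Summarise the distance by its median and 95th percentile, overall and by site and subgroup (synopsis and section 7.7.2). At an assumed SD of 0.3 D these would be 0.35 and 0.79 D.
3. In section 7.7.4, state how the vector value is formed from a single LFR-260 reading, or replace that ICC with the component ICCs plus the within-pair distance. Bring the synopsis into line.
4. Optional: the sphere-cylinder distance does not register axis error, which is analysed separately. The components M = S + C/2, J0 = -(C/2)cos(2A) and J45 = -(C/2)sin(2A), and the distance built from them, could be used instead. The components are signed and exist for every reading, so they suit both Bland-Altman and the ICC.

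The cost is SAP and synopsis wording only. Section 4.3 already has sphere, cylinder and axis recorded for both refractions, so no new data are needed.
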